## REVISION HISTORY

Version/Date	Modified by	Reason for Modifications
Final v1.0/23Oct2019	NA	
Final v1.1/03Aug2020	██████████	
 
1. To add the handling for patients whose baseline s-BA <math>\leq 70</math> <math>\mu\text{mol/L}</math> and for patients whose baseline pruritus score is <math>\leq 1</math>.
 
2. To add responder analysis based on the clinically meaningful threshold by using monthly scores. To add the result of clinically meaningful change from the blinded psychometric analysis.
 
3. To clarify off-treatment pruritus assessments will be included for analysis. For completers, the denominator to calculate US primary endpoint will be based on the last eDiary report day.
 
4. To update dictionary version.
 
5. To clarify the worst scenario will be used for tipping point analysis of EU and ROW primary endpoint.
 
6. To clarify the growth analysis will be based on derived growth data using the software or methods from the Centers for Disease Control and Prevention (CDC) website for patients with age <math>\geq 2</math> years old and from the WHO website for patients with age <math>< 2</math> years old. Also, to add a MMRM analysis.
 
7. To clarify the counting of number of adverse events. To add the adverse events of interest and their definitions.
 
8. To clarify that local laboratory data will be used when central laboratory data are not available.
 
9. To clarify the calculation of change from baseline for AM&PM pruritus scores (daily, weekly, bi-weekly, monthly) for analysis purposes.
 
10. To update the analysis windows of assessments.
 

Final v1.2/25Aug2020		

1, To remove completer analysis set and its analysis.

2. To add MMRM analysis for s-BA and ALT.

3. To clarify the handling for treatment completers in responder analyses.

----------------------	--	--

## LIST OF ABBREVIATIONS

The following abbreviations will be used within this SAP.

Abbreviation or special term	Explanation
E	Adverse Event
AFP	Alfa-fetoprotein
ALP	Alkaline Phosphatase
ALT	Alanine Aminotransferase
APRI	AST to Platelet Ratio Index
ANCOVA	Analysis of Covariance
AST	Aspartate Aminotransferase
ATC	Anatomical Therapeutic Chemical
BMI	Body Mass Index
BSEP	Bile Salt Export Pump
CAP	Controlled Attenuation Parameter
CDC	Centers for Disease Control and Prevention
CI	Confidence Interval
CMH	Cochran-Mantel-Haenszel
COVID-19	Coronavirus Disease 2019
CRO	Contract Research Organization
CSR	Clinical Study Report
DSMB	Data Safety and Monitoring Board
eCRF	Electronic Case Report Form
EOT	End of Treatment
EU	European Region
FAS	Full Analysis Set
eDiary	Electronic Diary
GGT	Gamma Glutamyl Transferase
GIC	Global Impression of Change
GIS	Global Impression of Symptoms
ICF	Informed Consent Form
ICH	International Conference on Harmonisation
████	████████████████████
INR	International Normalized Ratio
IWRS	Interactive Web Response System

Abbreviation or special term	Explanation
kg	Kilogram
MAR	Missing at Random
MCMC	Markov Chain Monte Carlo
MedDRA	Medical Dictionary for Regulatory Activities
MELD	Model for End-Stage Liver Disease
MI	Multiple Imputation
MMRM	Mixed-Effect Model for Repeated Measures
MNAR	Missing Not at Random
ObsRO	Observer-Reported Outcome
p-C4	Plasma 7 $\alpha$ -hydroxy-4-cholesten-3-one Concentration
PD	Protocol Deviation
PFIC	Progressive Familial Intrahepatic Cholestasis
PELD	Pediatric End-Stage Liver Disease
PedsQL	Pediatric Quality of Life Inventory
PK	Pharmacokinetics
PMM	Pattern Mixture Model
PP	Per Protocol
PRO	Patient-Reported Outcome
PT	Preferred Term
QoL	Quality of Life
RoW	Rest of World
SAE	Serious Adverse Event
SAP	Statistical Analysis Plan
SAF	Safety Analysis Set
SAS	Statistical Analysis System
s-BA	Serum Bile Acid
SD	Standard Deviation
SI	International System of Unit
SOC	System Organ Class
TEAE	Treatment Emergent Adverse Event
TFLs	Tables, Figures and Listings
ULN	Upper Limit of Normal
US	United States

## **1 INTRODUCTION**

The purpose of this Statistical Analysis Plan (SAP) is to provide detailed descriptions of the statistical methods, data derivations, and data displays for study protocol A4250-005 “A Double-Blind, Randomized, Placebo-Controlled, Phase 3 Study to Demonstrate Efficacy and Safety of A4250 in Children with Progressive Familial Intrahepatic Cholestasis Types 1 and 2 (PEDFIC 1)”. The table of contents and templates for the Tables, Figures and Listings (TFLs) will be produced in a separate document.

Any deviations from this SAP will be described and justified in the Clinical Study Report (CSR). The preparation of this SAP has been based on International Conference on Harmonisation (ICH) E3 and E9 guidelines [1, 2]. All data analyses and generation of TFLs will be performed using SAS® version 9.4 or higher. The SAP will be finalized and signed off prior to locking the database and unblinding.

## **2 STUDY OBJECTIVES**

### **2.1 Primary objectives**

To demonstrate the efficacy of repeated daily doses of 40 µg/kg/day and 120 µg/kg/day odevixibat (A4250) in children with progressive familial intrahepatic cholestasis (PFIC) Types 1 and 2, as determined by the following:

- The proportion of patients experiencing at least a 70% reduction in fasting serum bile acid (s-BA) concentration from Baseline to end of treatment or reaching a level  $\leq 70$  µmol/L after 24 weeks of treatment
- The proportion of positive pruritus assessments at the subject level over the 24-week treatment period. A positive pruritus assessment is defined as a scratching score of  $\leq 1$  or at least a one-point drop from baseline on the Albireo Observer-Reported Outcome (ObsRO) instrument

### **2.2 Secondary objectives**

- To evaluate the effect of odevixibat on serum alanine aminotransferase (ALT) concentration
- To evaluate the effect of odevixibat on growth
- To evaluate the effect of odevixibat on sleep disturbance
- To evaluate the effect of odevixibat on the need for surgical treatment (biliary diversion or liver transplantation)
- To assess the safety and tolerability of repeated daily doses of odevixibat for 24 weeks

## 3 STUDY DESIGN

### 3.1 General study design

This is a double-blind, randomized, placebo-controlled, Phase 3 study to investigate the efficacy and safety of 40 µg/kg/day and 120 µg/kg/day of odevixibat compared to placebo in children with PFIC Type 1 and 2.

The study includes a 35- to 56-day Screening Period followed by a 24-week Treatment Period and a 4-week Follow-Up Period. After completion of the Screening Period, eligible patients (20 per treatment group) will be randomized on Day 0 (Visit 3) in a 1:1:1 fashion to receive 40 µg/kg/day or 120 µg/kg/day of odevixibat, or a matching placebo. Study data will be periodically reviewed by an unblinded Data Safety and Monitoring Board (DSMB).

A total of approximately 60 patients with a clinical diagnosis of PFIC Type 1 or 2 that have been genetically confirmed will be randomized. The randomization will be done in blocks and stratified according to PFIC type (Type 1 and 2) and age category (6 months to 5 years, 6 to 12 years, and 13 to ≤18 years) to ensure approximate balance between dose schemes (1:1:1).

The study will target 15% of enrolled patients to be PFIC-1 patients. If enrollment of all PFIC-2 patients is completed and the 15% enrollment of PFIC-1 patients has not yet been achieved, then enrollment of PFIC-2 patients will continue to reach the total study target enrollment. An attempt will be made to randomize a minimum of 10 patients from each age category (6 months to 5 years, 6 to 12 years, and 13 to ≤18 years). A maximum of 5 patients that were treated in Study [A4250-003](#) will be allowed to participate in this study.

Patients who complete the Treatment Period and Visit 9 (Day 168, Week 24) in this study will be invited to participate in a 72-week open-label extension study ([A4250-008](#), EudraCT Number 2017-002325-38, subject to a separate study approval) in which all patients will receive odevixibat 120 µg/kg/day. Prior to [protocol amendment 6](#), patients who had completed at least 12 weeks of the Treatment Period and had either no improvement or intolerable symptoms were eligible to complete the End of Treatment (EOT) Visit and were offered the opportunity to enter Study [A4250-008](#).

There will be up to 10 clinic visits during the study and one scheduled telephone contact, as follows:

- Visit 1: Screening Period start. Patient is considered enrolled after signing the informed consent form (ICF) (Days -56 to -35)
- Visit 2: Screening Visit 2 (Days -28 to -7)
- Visit 3: Randomization Visit (Day 0)
- Telephone Contact 1: (Day 14 - Week 2)
- Visit 4: Clinic Visit (Day 28 - Week 4)
- Visit 5: Clinic Visit (Day 56 - Week 8)
- Visit 6: Clinic Visit (Day 84 - Week 12)
- Visit 7: Clinic Visit (Day 126 - week 18)
- Visit 8: Clinic Visit (Day 154 - Week 22)

- Visit 9: Clinic Visit, End of Treatment (Day 168 - Week 24)
- Visit 10: Follow-Up Visit, 28 days after last dose of study drug (Day 196). Patients continuing in Study A4250-008 will not have this follow-up visit.

Additional clinical visits may be required for patients who need direct site assistance, e.g., due to adverse event (AE) monitoring, to fulfill screening requirements, and/or for safety maintenance.

Caregivers/patients will be instructed on the daily use of the eDiary. The eDiary will include patient-reported outcome (PRO) for patients  $\geq 8$  years of age and observer-reported outcome (ObsRO) instruments for evaluation of itching (PRO), scratching (ObsRO), and sleep disturbance (PRO and ObsRO) during the Screening Period (study Days -56 to 0), throughout the 24-week Treatment Period (study Days 0 to 168), and Follow-up (Day 196). Additionally, caregivers will be requested to use the eDiary to report the time each dose of study drug is administered during the Treatment Period. All entries made in the eDiary are transmitted overnight to the database which can be accessed via Trial Manager.

The study nurse will monitor eDiary compliance by routine review of the Trial Manager website. If both diary entries on a day are missing, the study nurse will call the patient/caregiver to remind them to complete all scheduled entries. Any noncompliance will be documented and explained in the source documents.

### **3.2 Randomization and blinding**

A double-blind design is employed so that both the investigators and the patients will be unaware of the treatment assignment during the study. The sponsor and contract research organization (CRO) personnel (except CRO statisticians generating the list of randomization codes) involved in this study will also not be aware of the treatment assignment during the study.

After written informed consent/assent is obtained from an eligible patient/legal guardian, an 8-digit patient identification number will be assigned. The first 2 digits will denote the country, followed by a 3-digit site number and a 3-digit patient sequence number. This number will be created and allocated by the Interactive Web Response System (IWRS), when the patient first enters the system at screening. The randomization codes will be computer-generated by an [REDACTED] biostatistician and kept by an unblinded statistician [REDACTED] independent from the project team. The randomization will be done in blocks and stratified according to PFIC type (Type 1 and 2) and age category (6 months to 5 years, 6 to 12 years, and 13 to  $\leq 18$  years) to ensure approximate balance between dose schemes (1:1:1). A separate randomization list will be prepared for the maximum of 5 patients from Study [A4250-003](#) regardless of stratification. Randomization codes will be assigned sequentially as patients become eligible for randomization.

Patients who are eligible for randomization will be assigned a unique 4-digit randomization number by IWRS. This randomization number identifies which treatment will be allocated to

the patient. Patients who withdraw from the study after the randomization visit will not be replaced and their randomization number will not be reused.

To ensure blinding, the study drug and the matching placebo have the same shape and size. Patients will receive capsule(s) of odevixibat according to their assigned dose group or capsule(s) of matching placebo once a day during the double-blind Treatment Period. Labels on the study drug containers will not identify the treatment to which a patient is randomized. Traceability of the treatment is ensured by the study drug number.

The IWRS system will assign a study drug number(s) corresponding to the randomization arm at each dispensing visit. The 5-digit study drug number will identify study drug packs and will be detailed on the study drug label. Dispensing of study drug will be coordinated by IWRS.

### 3.3 Study treatments and assessments

There will be three treatment groups in this study.

- Odevixibat 40 µg/kg/day group
- Odevixibat 120 µg/kg/day group
- Placebo group

Odevixibat and placebo will be supplied as capsules for oral administration. Study drug is to be taken once daily on Day 1 through Day 168 as described in [Protocol Section 8.2](#).

Study drug will be dispensed to the patient at Visits 3, 4, 5, 6, 7, and 8, together with instructions on how to store and take the drug. Study drug administration data, including whether each patient took each dose or partial doses of study drug, whether there were any delayed or missed doses, and whether the capsule was opened or swallowed whole will be documented through the eDiary and transferred to the clinical study database.

The number of capsules provided to the patient will be based on body weight at Visit 3. At Visit 6, if a patient's weight has shifted to another weight category (identified in [Protocol Table 2](#)), the number of capsules per day may be adjusted.

Odevixibat should be taken in the morning, together with food. On clinic visit days when laboratory assessments are conducted, study drug should be taken after the visit and after laboratory samples are taken. The last dose of study drug will be administered the day before Visit 9. At Study Visit 9, the patient has the option to enroll in an open-label extension study (A4250-008) should they meet the required entry criteria. If the patient is continuing into Study A4250-008 this will be the last visit in this study and the first visit in Study A4250-008. Visit 9/EOT should also be performed if the patient is prematurely withdrawn from the study.

Clinic Visit 10 will take place 28 days after Visit 9 for patients not continuing into Study A4250-008. A patient who withdraws from treatment prematurely and does not enter Study A4250-008 will have EOT (Visit 9) assessments at the time of withdrawal and a follow-up

assessment (Visit 10) 28 days following the last dose of study drug, and the patient will be recorded as withdrawn.

Efficacy assessments and daily recording of pruritus using an electronic diary (eDiary) in this study are briefly introduced as follows.

### **Serum Bile Acids**

Blood samples for analysis of fasting total s-BA will be drawn at all visits. Samples will be processed and transported to a central laboratory per instructions in the laboratory manual. Patients will fast (water intake only is permissible) for at least 4 hours prior to the collection of samples for s-BA. Exceptions can be made for infants, <12 months of age, if unable to fast for the full 4 hours. For any visit at which a bile acid sample result is unreportable, an additional unscheduled visit for a repeat sample collection may be scheduled. All s-BA results during the treatment period and follow-up will be blinded.

### **Itching, Scratching and Sleep Score**

Itching, observed scratching, and sleep disturbance will be recorded twice each day via eDiary. Patients and/or caregivers will be instructed to complete the eDiary every day throughout the study in the morning after the patient wakes up and, in the evening, just before the patient goes to sleep. Patients and caregivers will receive a formal training session during Visit 1.

The eDiary includes Albireo ObsRO and PRO items. Patients <8 years of age will not be asked to complete the Albireo PRO items; only the Albireo ObsRO will be completed by caregivers of patients in this age group. Older patients, 8 to 18 years of age, will complete the Albireo PRO items and the caregiver will complete the Albireo ObsRO items. The Albireo PRO items assess severity of itch, aspects of sleep disturbance (morning diary only), and tiredness. For patients 8 to 12 years of age, the caregiver will read the Albireo PRO items along with the child and record the child's response. A guide will be provided to the caregivers that provides standardized explanations of the Albireo PRO items, in case the patient is confused or requires clarification about the meaning of a question. The Albireo ObsRO items assess severity of observed scratching, aspects of observed sleep disturbance (morning diary only) and observed signs of tiredness (evening diary only). The Albireo ObsRO and PRO scratching and itch severity items use 0 to 4 response scales, where each response is distinguished by a unique facial expression, verbal anchor, number, and color code ([Protocol Appendix 2](#)).

### **Growth**

Growth will be measured as height (velocity) and weight (Z-score) using a certified weight scale at Visits 1, 3, 6 and 9. BMI will be calculated by weight (kg) / height (m^2). Change will be defined as linear growth deficit (weight and BMI for age) compared to standard growth curve (Z-score, standard deviation from the 50th percentile [SD from P50]).

## Quality of Life Questionnaire (PedsQL)

Patients and caregivers will be asked to complete a QoL questionnaire (PedsQL) at Visit 3 and Visit 9. Details of the questions included on the questionnaire are provided in [Protocol Appendix 4](#).

## Biomarker

Blood samples for autotaxin and p-C4 will be drawn at Visits 3, 4, and 9 for children with body weight >10 kg.

## PELD/MELD Score

At randomization and EOT, pediatric end-stage liver disease (PELD) score will be calculated for children under 12 years of age. For children 12 years or older, the (model for end-stage liver disease) MELD score will be calculated.

PELD Score =  $4.80 * \ln(\text{total bilirubin}) + 18.57 * \ln(\text{INR}) - 6.87 * \ln(\text{albumin}) + 4.36$  (if patient <1 year: scores for patients listed for liver transplantation before the patient's first birthday continue to include the value assigned for age (<1 year) until the patient reaches the age of 24 months) + 6.67 (if the patient has growth failure [ $< -2\text{SD}$ ])

Laboratory values less than 1.0 will be set to 1.0 for the calculation of the PELD score.

MELD Score =  $9.57 * \ln(\text{creatinine}) + 3.78 * \ln(\text{total bilirubin}) + 11.2 * \ln(\text{INR}) + 6.43$   
Laboratory values less than 1.0 will be set to 1.0 and serum creatinine values greater than 4.0 mg/dL (equivalent of 353.6  $\mu\text{mol/L}$ ) will be set to 4.0 for calculation of the MELD score.

For calculation of the PELD/MELD score [3] laboratory parameters will be converted (if necessary) into the following units:

- Total Bilirubin in mg/dL
- Albumin in g/dL
- Creatinine in mg/dL

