### Markers of Fibrosis

APRI score and Fib-4 score will be calculated at randomization and at end of treatment.

APRI = [(AST in U/L) / (AST ULN in U/L)] × 100 / (Platelets in 10^9/L)

Fibrosis 4 Score = (Age\*AST in U/L) / (Platelets in 10^9/L \* √(ALT in U/L)).

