### 4.3 Exploratory endpoints

Exploratory efficacy endpoints include the following:

- Assessment of Global Symptom Relief at Weeks 4, 12, and 24 as measured by patient, caregiver, and clinician via the global impression of change (GIC) item
- Change from baseline in fasting s-BA at Week 4
- Change in pruritus, as indexed by caregiver-reported observed scratching, from baseline by each 4-week interval of the Treatment Period as measured by the Albireo ObsRO instrument
- Change from baseline by each 4-week interval of the Treatment Period in patient-reported and observer-reported night time itching and scratching severity scores, respectively, as measured by the Albireo PRO and ObsRO instruments.
- Change from baseline by each 4-week interval of the Treatment Period in patient-reported and observer-reported morning time itching and scratching severity scores, respectively, as measured by the Albireo PRO and ObsRO instruments.
- Change from baseline by each 4-week interval of the Treatment Period in pooled pruritus score including observer-reported scratching for patients  $< 8$  years of age and patient-reported itch severity for patients  $\geq 8$  years of age, as measured by the Albireo PRO and ObsRO instruments, respectively.
- Change from baseline by each 4-week interval of the Treatment Period in additional patient-reported and observer-reported sleep parameters (e.g. tiredness and number of awakenings), as measured by the Albireo PRO and ObsRO instruments, respectively.
- Change from baseline to Week 24 in PedsQL
- Change from baseline in serum ALT concentration at Week 4

- Change from baseline in total bilirubin at Weeks 4, 12, and 24
- Change from baseline in AST and gamma-glutamyl transferase at Weeks 4, 12, and 24
- Change from baseline for other biochemical markers and measures of bile acid synthesis (autotaxin, plasma 7 $\alpha$ -hydroxy-4-cholesten-3-one concentration [p-C4]) at Week 24
- Change in paediatric end-stage liver disease/model for end-stage liver disease (PELD/MELD) score, AST to platelet ratio index (APRI) score, and Fib-4 score from baseline to Week 24
- Change from baseline to Week 24 in stage of liver fibrosis as assessed by Fibroscan® (where available)
- For patients who answered Yes to Questions 1 and 2 in the exit survey, changes from baseline in the average scratching score based on the Albireo ObsRO instrument in the last 2 weeks before treatment termination

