### 8.6.5 Analyses of exploratory endpoints

The exploratory efficacy variables are listed in Section 4.3. All the exploratory analyses will be based on the FAS.

Exploratory variables including Global Symptom Relief, biochemical markers and measures of bile acid synthesis, Albireo PRO and ObsRO itching/scratching severity scores, additional Albireo PRO and ObsRO sleep parameters, PELD/MELD score, APRI score, and the Fib-4 score will be analyzed descriptively for categorical and continuous data. For continuous data, the change from baseline will be analyzed in addition to the presentation of actual visit values. For Albireo PRO and ObsRO itching/scratching severity scores, unrounded baseline will be used to calculate change from baseline. For categorical data, shift tables or frequency and percentages of patients will be presented as appropriate. A line graph of itching/scratching daily severity scores of Albireo PRO and ObsRO over time for each patient will be provided.

For continuous data, such as PELD/MELD score, APRI score, and Fib-4 score, biochemical markers and measures of bile acid synthesis, the change from baseline to Week 24 will be analyzed descriptively in addition to the actual visit values. Global Symptom Relief data at Weeks 4, 12, and 24 will be summarized as categorical variables. Time points (visit window) are specified in [Appendix B](#).

Comparisons of the change from baseline at Week 24 in the PedsQL total score (calculated as average score of all answered items) between the treatment groups will be conducted using analysis of covariance (ANCOVA). The model will include terms for baseline, PFIC type, age category, and treatment. The analysis will be conducted based on the total scores reported by child ( $\geq 5$  years of age) and by parent (only including patients  $\geq 5$  years of age) separately. If the sample size based on child reported data ( $\geq 5$  years of age) is less than 10, then ANCOVA will not be conducted. The PedsQL total score of the family impact module will be analyzed similarly. The total score and the domain scores will be summarized descriptively.

Change from baseline to Week 24 in stage of liver fibrosis measured by Fibroscan® will be analyzed descriptively. The frequencies of stages may be summarized by shift tables. Steatosis grade analysis will be performed in a similar fashion.

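### The choice between PELD and MELD, and the PELD under-1-year term, are re-applied at end of treatment, so a first or twelfth birthday during the trial changes the score with no change in the liver

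*SAP*

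**What the plan says.** SAP Section 3.3 (PELD/MELD Score) ties the calculation to two visits: "At randomization and EOT, pediatric end-stage liver disease (PELD) score will be calculated for children under 12 years of age". It continues: "For children 12 years or older, the (model for end-stage liver disease) MELD score will be calculated". The PELD formula carries two additive terms besides the laboratory values: 4.36 if the patient is under 1 year, and 6.67 if there is growth failure. Only children listed for transplantation before their first birthday "continue to include the value assigned for age (<1 year) until the patient reaches the age of 24 months". MELD has neither term and has a constant of 6.43.

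Section 4.3 makes the change in PELD/MELD, APRI "and Fib-4 score from baseline to Week 24" an exploratory endpoint. Section 8.6.5 names PELD/MELD among the continuous variables for which "the change from baseline to Week 24 will be analyzed descriptively in addition to the actual visit values".

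For Fib-4, Section 3.3 (Markers of Fibrosis) says "APRI score and Fib-4 score will be calculated at randomization and at end of treatment". The formula begins "Fibrosis 4 Score = (Age\*AST in U/L" and gives no date for the age.

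Nothing in the SAP fixes the formula or the infant term at baseline, or says how to form a change for a child scored by PELD first and MELD later. Section 9, item 2(j), corrects the PELD and APRI formulas but does not touch this.

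**The concern.** A change from baseline is interpretable only if the same quantity is measured twice. Here the instrument is chosen by age at each visit, and patients enter from 6 months to 18 years (Section 3.1), so both the 1-year and the 12-year cut points lie inside the population. A child who crosses one of them during the 24 weeks gets a shift that reflects a birthday.

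The two shifts have opposite signs: apparent improvement at age 1 and apparent worsening at age 12. Stratification by age category does not balance them reliably. Infants share a stratum with children up to 5 years, and 11-year-olds share one with children from 6 years. The analysis is descriptive, so no model term absorbs the shift. With about 20 patients per arm, one or two such children can visibly move an arm mean.

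**Working it through.** The SAP states no figure that depends on this, so there is nothing to reproduce. The check holds all laboratory values constant and changes only age.

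**Inputs from the SAP**
- PELD = 4.80 ln(bilirubin) + 18.57 ln(INR) − 6.87 ln(albumin) + 4.36 (if under 1 year) + 6.67 (if growth failure).
- MELD = 9.57 ln(creatinine) + 3.78 ln(bilirubin) + 11.2 ln(INR) + 6.43.
- Laboratory values below 1.0 are set to 1.0 in both scores, so creatinine of at most 1.0 mg/dL contributes 0.
- Interval: 168/365.25 = 0.46 years. About 60 patients, 20 per arm.

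**Assumed inputs** (not in the SAP): bilirubin 3 mg/dL, INR 1.2, albumin 3.8 g/dL, creatinine at most 1.0 mg/dL. The grid for the range is bilirubin 1 to 10, INR 1.0 to 1.5 and albumin 3.0 to 4.5.

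**Twelfth birthday**
- PELD = 4.80 ln 3 + 18.57 ln 1.2 − 6.87 ln 3.8 = 5.27 + 3.39 − 9.17 = −0.51.
- MELD = 0 + 3.78 ln 3 + 11.2 ln 1.2 + 6.43 = 4.15 + 2.04 + 6.43 = 12.62.
- Switch: 12.62 − (−0.51) = +13.1.

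In general, with creatinine at the floor, the switch is 6.43 − 1.02 ln(bilirubin) − 7.37 ln(INR) + 6.87 ln(albumin), less 6.67 if the growth-failure term applied at baseline.

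| Bilirubin, INR, albumin | No growth failure | Growth failure at baseline |
|---|---|---|
| 10, 1.5, 3.0 (grid minimum) | +8.64 | +1.97 |
| 3, 1.2, 3.8 | +13.14 | +6.47 |
| 1, 1.0, 4.5 (grid maximum) | +16.76 | +10.09 |

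Effect of one such child on a 20-patient arm mean, without growth failure: 8.64/20 = 0.43 to 16.76/20 = 0.84. With growth failure: 0.10 to 0.50.

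**First birthday, child not listed for transplantation**
- The change is −4.36 whatever the laboratory values, or −4.36/20 = −0.22 on an arm mean.

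**How many children** (assuming ages uniform from 0.5 to 18 years)
- Crossing age 12: 60 × 0.46/17.5 = 1.6 in the whole trial.
- Crossing age 1: the same arithmetic gives 1.6, less any who are listed. A younger intake would raise this.

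**Fib-4**
- The score is linear in age. If age at each visit were used, the ageing increment would be 0.46 × AST/(platelets × √ALT), which does not contain the child's age. With assumed AST 100, ALT 100 and platelets 250, it is 0.46 × 100/(250 × 10) = 0.018, the same at 6 months and at 12 years.

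**After the fix**
- With formula, infant term and Fib-4 age held at their randomization values, age alone changes every score by 0.

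**The case against.** The strongest reply is about weight. These are exploratory endpoints, summarized descriptively beside the visit values, with no test or decision attached. Few children cross a cut point. The SAP never says in words that a PELD value is to be subtracted from a MELD value. Other liver measures are planned that have no age term, including ALT as a secondary endpoint with an MMRM, and APRI. Most of this stands and limits the point to a minor one. It does not remove it: Section 8.6.5 treats PELD/MELD as a single continuous variable, with no separation or exclusion, and a programmer following it would form that difference.

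Some stronger readings are tempting and should not be drawn.
- A reader might infer that Fib-4 rises sharply in infants and that arms will differ by their share of infants. The planned scale is absolute change, on which the ageing increment does not depend on the child's age; large percentages would come only from dividing by a near-zero baseline. A common drift in all arms would also largely cancel against placebo. Nor does the SAP say that age at the visit is used: its only defined age variable is in Appendix A under demographic and baseline characteristics, and using that one value twice would give no drift.
- A reader might infer that every score has an age term. MELD has none; only the choice of formula depends on age.
- A reader might infer that the artefact exceeds any plausible treatment effect. The SAP gives no expected effect or standard deviation for these scores, so that cannot be judged.

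**Conclusion.** The concern holds for PELD/MELD as a minor flaw. The rule in Section 3.3, combined with the change endpoint in Sections 4.3 and 8.6.5, gives a false worsening of about 13 points at age 12 (about 9 to 17 without growth failure, down to 2 with it) and a false improvement of 4.36 points at the first birthday of an unlisted infant. The age-12 sizes rest on assumed laboratory values and on creatinine of at most 1.0 mg/dL; a higher value would enlarge the switch. The 4.36 rests on the SAP alone. The expected count of one to two children of 60 at age 12 rests on an assumed uniform age distribution. For Fib-4 there is only an unstated reference date for age, which needs a clarification. No primary or secondary conclusion depends on any of this.

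**What to change.** Add to Section 8.6.5 or Appendix A: when change from baseline is computed, the formula (PELD or MELD) and the under-1-year term that apply at randomization are used at both time points; changes in PELD and in MELD are summarized separately; and scores at current age are listed. For Fib-4, state that age at randomization is used at both time points, preferably in decimal years, since completed years would make the score zero for a child under 1.

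The cost is a sentence or two and a small derivation change, using data already collected. The downsides are that the end-of-treatment value used for change will differ from the bedside score in a few children, and that separate PELD and MELD summaries will rest on smaller groups.
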